4. DETERMINATION OF SAMPLE SIZE

Based on the initial data obtained to date and data in the literature, it is anticipated that approximately 50% of subjects hospitalized with PCR-positive SARS-CoV-2 infections (WHO COVID-19 Classification level 3 or 4) will experience treatment failure at day 28 from enrollment. Treatment failure is defined as progression to WHO COVID-19 classification level of 6 or greater as defined by one or more of the following: the need for high-flow oxygen or non-invasive ventilation, the need for intubation or mechanical ventilation (level 6), the need for ECMO (level 7), or any cause death (level 8); the initiation of a non-study immune modulator; withdrawing consent from the study; becoming lost to follow-up; or discontinuation of treatment for any reason other than renal function or pregnancy. The sample size estimate for this proof of concept is based on Fisher's Exact two-sided test for 2 proportions using NQuery 8 (www.statsols.com). Estimates of admitted patients requiring salvage therapy is unknown, however, the clinical data set who require intubation is a likely subset of those whose condition worsens but do not progress to respiratory compromise.

Although the interim analysis will utilize masked treatment assignments, the O'Brien Fleming group sequential sample size estimation confirms that a single interim look would retain a cumulative exit probability of 70% with a cumulative alpha =0.05 after the final analysis using the target enrollment of 132 (44 per group) to detect a reduction of those reaching the endpoint of treatment failure. This study is not powered to assess statistically significant differences between GLS-1027 doses. A gate-keeping method will be used to compare the highest dose to placebo first and then compare the lower dose if the higher dose shows significant benefit.

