Clinically, each of the pathogenic coronaviruses cause lower respiratory tract illness. For SARS-CoV-2, clinical illness typically starts with a viral prodrome characterized by malaise, muscle aches, and headache that can progress to a febrile illness with diaphoresis. Less usual, but pathognomonic signs are anosmia, ageusia, conjunctivitis, and perniosis. While most individuals will recover, progression to increasing respiratory compromise requiring oxygenation, high-flow oxygenation, intubation and mechanical ventilation, extracorporeal mechanical oxygenation (ECMO), or death may occur. Other complications of severe disease include renal failure and arterial thrombosis that may present as stroke, myocardial infarction, or peripheral arterial obstruction. Early studies reported that approximately 50% of those who require supplemental oxygenation after admission to hospital progress to needing mechanical ventilation at some time during hospitalization ^[1]. It is generally considered that as the level of acuity of admitted patients has increased, this percentage of those progressing to severe disease is likely higher. The mortality rate of those requiring mechanical ventilation has been reported as 50-80% ^[1] including recent data reported from New York City. Risk factors for severe disease and death include older age, diabetes mellitus, hypertension, cardiac disease, and chronic obstructive pulmonary disease. As was reported for both SARS-CoV and MERS-CoV, the fatality rate in men exceeds that for women.

Pulmonary disease associated with SARS-CoV-2 infection is characterized by a marked inflammatory component that was not described for either SARS-CoV or MERS-CoV. In fact, at presentation, minimally symptomatic patients may present with marked interstitial inflammatory changes on chest radiography presenting as "white-out" as described by colleagues treating infected patients in Seoul, Korea. Of interest, a similar presentation of severe pulmonary inflammatory disease despite a relatively low level of virus has been observed in ferrets). This inflammatory pneumonitis has been ascribed inflammatory

cytokine release. related to the release of multiple cytokines including TNF α , IL-1 β , IL-6 and can lead to capillary leakage, hypotension, and myocardial dysfunction.

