4. SELECTION AND ENROLLMENT OF PARTICIPANTS

4.1 Recruitment of Participants

4.2 Inclusion Criteria for enrollment

- 1. Age 18 years or older
- 2. Able to provide informed consent
- 3. Able and willing to comply with study procedures
- 4. Enrollment within 72 hrs of hospitalization with a diagnosis of PCR confirmed SARS-CoV-2 infection
- 5. WHO COVID-19 classification level of 3 or 4

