4.3 Exclusion Criteria for enrollment

- 1. Pregnant or lactating
- 2. SpO2 less than 90% on room air or less than 95% on supplemental oxygen
- 3. Calculated GFR < 60 (Cockcroft-Gault)
- 4. Meets hospital treatment algorithm for treatment with dexamethasone at a dose of 6 mg/day for a 10 day course. A single bolus dose of 6 mg of dexamethasone given in the

Emergency Department and continued at a dose of \leq 3.5 mg/day or less is allowed.

- 5. Meets treatment algorithm criteria for treatment with toclizumab or other anti-IL-6 agent
- 6. Treatment with an anti-IL-6 inhibitor, anti-IL-1 inhibitor, anti-TNF monoclonal antibody, or anti-JAK inhibitor (see Appendix A for exclusionary period for individual drugs)
- 7. Participation in a COVID-19 clinical trial that includes prescription of a drug with anticytokine activity
- 8. Treatment within the past 60 days with a chemotherapeutic agent
- Current outpatient treatment with systemic corticosteroids at a dose equivalent of 20 mg/day or greater of prednisone or prednisolone, 16 mg/day or greater of methylprednisolone
- 10. Diagnosis of leukemia or lymphoma
- 11. WHO COVID-19 classification level of 5 or greater (use of high-flow oxygen, nonmechanical ventilation such as CPAP, mechanical ventilation)

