8.2 Sample Size

Based on the initial data obtained to date and data in the literature ^[1], it is anticipated that approximately 50% of subjects hospitalized with PCR-positive SARS-CoV-2 infections

(WHO COVID-19 Classification level 3 or 4) will progress to WHO COVID-19 classification level of 6 or greater as defined by one or more of the following: the need for intubation or mechanical ventilation (level 6), the need for ECMO (level 7), or any cause death (level 8). The sample size estimate for this proof of concept is based on Fisher's Exact two-sided test for 2 proportions using NQuery 8 (www.statsols.com). Estimates of admitted patients requiring salvage therapy is unknown, however, the clinical data set who require intubation is a likely subset of those whose condition worsens but do not progress to respiratory compromise.

Although the interim analysis will utilize masked treatment assignments, the O'Brien Fleming group sequential sample size estimation confirms that a single interim look would retain a cumulative exit probability of 70% with a cumulative alpha =0.05 after the final analysis using the target enrollment of 132 (44 per group) to detect a reduction of those reaching the endpoint of treatment failure, which includes advancing to WHO COVID-19 Classification level \geq 6 from 50% (SOC treated) to 25% in either treatment group of SOC plus GLS-1027. Other conditions also qualify a subject as treatment failure include: need for salvage therapy with IL-6 monoclonal antibody; or institution of salvage therapy with dexamethasone (\geq 6 mg/day), withdrawing consent from the study, becoming lost to follow-up, or discontinuation of treatment for any reason other than renal function or pregnancy. This study is not powered to assess statistically significant differences between GLS-1027 doses.

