13. APPENDICES

Note 1: This appendix may be updated through the clinical trial as new agents are either approved or brought into clinical practice. The time prior to enrollment that each drug is to be excluded is listed, but may be updated if new information is published regarding modifications to drug half-life.

Note 2: The decision to initiate treatment with any of the agents listed below is determined either according to the hospital specific SARS-CoV-2 Treatment Algorithm or per individual physician decision. If any agent is started post-enrollment, use should be documented as a concomitant medication. Other study procedures should continue as per the schedule of events.

GeneOne Life Science, Inc.

PATIENT STATE	DESCRIPTOR	SCORE 0
Uninfected	No clinical or virologic evidence of infection	
Ambulatory	Infected, with no limitation of activities	1
	Infected, with limitation of activities	2
Hospitalized	No oxygen therapy	3
Mild disease	Oxygen by mask or nasal canula	4
Hospitalized	Non-invasive ventilation or high-flow oxygen	5
Severe disease	Intubation with mechanical ventilation	6
	Ventilation plus any of vasopressor Rx, RRT, ECMO	7
Death	Death	8

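### The 50% control rate has a described source only for oxygen-requiring patients reaching ventilation, yet it serves a wider population and two endpoints; the stated 70% power is not secure.

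*SAP*

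**What the plan says.** Protocol 1.1 reports from early studies (reference 1) that "approximately 50% of those who require supplemental oxygenation after admission to hospital progress to needing mechanical ventilation at some time during hospitalization".

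Protocol 8.2 takes about 50% as the share of level 3 or 4 inpatients who "will progress to WHO COVID-19 classification level of 6 or greater as defined by one or more of the following": ventilation, ECMO or death. It cites the same reference 1, preceded by the phrase "Based on the initial data obtained to date and data in the literature". Its next paragraph uses the same 50%, against 25% on treatment, for treatment failure, which also counts salvage therapy, withdrawal of consent, loss to follow-up and discontinuation.

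Eligibility (Protocol 4.2) is "WHO COVID-19 classification level of 3 or 4". The WHO scale in the protocol appendix describes level 3 as "No oxygen therapy". Protocol 4.3 excludes level 5 or greater and "SpO2 less than 90% on room air or less than 95% on supplemental oxygen".

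SAP 4 says that about 50% of level 3 or 4 inpatients "will experience treatment failure at day 28 from enrollment". Its definition of failure adds high-flow oxygen or non-invasive ventilation and any non-study immune modulator, and also counts withdrawal, loss to follow-up and discontinuation. It gives 132 patients (44 per group), 70% power, alpha 0.05 and a two-sided Fisher test, as the protocol does, but not the 25% target. Both documents say the rate of salvage therapy is unknown.

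**The concern.** One figure does three jobs: oxygen-requiring patients reaching ventilation (Protocol 1.1), level 3 or 4 patients reaching WHO level 6 or greater (Protocol 8.2), and level 3 or 4 patients failing on a composite (Protocol 8.2, second paragraph, and more broadly SAP 4). Patients not on oxygen lie outside the first group. The composite contains level 6 or greater, so its rate cannot be lower in the same patients, and it is higher as soon as anyone fails on an added component alone. Neither step comes with a reason for keeping 50%.

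What is at stake is how a null result is read. The 70% is the only power figure given, and it depends on the control rate, on the size of the effect, and on how many failures the drug could influence. SAP 4 names no target rate, so its power statement cannot be checked from the SAP alone.

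**Working it through.** **Inputs.** 44 per arm; two-sided alpha 0.05; Fisher's exact test; one O'Brien-Fleming look at 22 per group, so half the information (Protocol 8.2 and 8.8, SAP 4 and 5); 50% v 25% (Protocol 8.2). All powers are for one dose against placebo.

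**1. The plan's own figure.** Normal approximation, unpooled variance:

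- Standard error = √[(0.50×0.50 + 0.25×0.75)/44] = √(0.4375/44) = 0.0997.
- Expected z at the end = 0.25/0.0997 = 2.51.
- O'Brien-Fleming-type bounds at information 0.5 and 1: 2.772 and 1.979.
- Probability of crossing either bound = 70.4%.

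The stated 70% is reproduced. With pooled variance the group-sequential figure is 67.4%, and with a continuity correction 62.1%.

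**2. The test the plan names.** Sum the binomial probabilities of every pair of failure counts (0 to 44 in each arm) for which the two-sided Fisher p-value is at most 0.05. At 50% v 25% the power is 61.1%. The gap of about 9 points is due to the method. It would exist even if 50% were exactly right.

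**3. Other control rates, same exact method, relative reduction held at one half.**

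| Control v active | Fisher power |
|---|---|
| 30% v 15% | 29% |
| 35% v 17.5% | 37% |
| 40% v 20% | 45% |
| 45% v 22.5% | 53% |
| 50% v 25% | 61% |
| 55% v 27.5% | 68% |
| 60% v 30% | 74% |

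**4. How level 3 patients could move the rate (assumed shares and risk).** Blended rate = (1 − s)×0.50 + s×r, where s is the level 3 share and r their risk. The documents give neither.

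- s = 25%, r = 20%: 0.75×0.50 + 0.25×0.20 = 42.5%.
- s = 50%, r = 20%: 0.50×0.50 + 0.50×0.20 = 35%.

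**5. How drug-unrelated failures could move both rates (assumed).** Suppose 50% v 25% holds for WHO level 6 or greater, and a fraction q of the remaining patients in each arm fails for reasons the drug does not affect. Control = 0.50 + 0.50q; active = 0.25 + 0.75q.

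- q = 10%: 55% v 32.5%, power 47%.
- q = 20%: 60% v 40%, power 36%.

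These are no longer halvings: the relative reductions are 0.225/0.55 = 41% and 0.20/0.60 = 33%. Power falls because the effect is diluted, although the control rate has risen.

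**6. A case in the other direction.** If the absolute reduction of 25 points is kept, power rises as the control rate falls: 68% at 40% v 15%, and 85% at 30% v 5%.

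**The case against.** The strongest reply is that no direction of error has been shown. Patients not on oxygen would be expected to lower the rate. The added components raise it, and Protocol 1.1 itself argues that progression is probably more frequent than 50% as the acuity of admitted patients rises. A true halving from 60% has 74% power, above the stated figure. This stands. A reader might infer that the population mismatch shows 50% to be too high and power to be overstated on that account. The documents do not support that.

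Second, Protocol 8.2 and SAP 4 also rest on initial data. These are not shown and reference 1 was not available here, so one background sentence need not be the whole basis. This stands too: the documents do not establish that 50% is unsupported, only that the described source does not match.

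Third, the SAP cites protocol version 5.0 and a 14-day treatment period, whereas the supplied protocol has 28 days and may be another version. A reader might infer that the two uses of 50% are incompatible. That is not proven: an approximate 50% could have held for level 6 or greater under one version and for the composite under another. The shift of population and endpoint does, however, already occur within the supplied protocol, between 1.1 and the two paragraphs of 8.2.

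Fourth, Protocol sections 1 and 1.1 describe participants as requiring supplemental oxygen, so the level 3 share may be small. That may be so, but 4.2 admits level 3.

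Finally, this is a phase II proof of concept with no futility stop, and nothing in its analysis or error rate changes. That bears on how serious the point is, not on whether the stated power should be right.

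**Conclusion.** The concern holds as a gap in justification together with an insecure power figure. The described source of the 50% matches neither the population nor the endpoint to which it is applied, and SAP 4 carries it to a broader composite with the sample size and power unchanged and the target rate missing.

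Two results should be kept apart. The fall from 70% to 61% at 50% v 25% needs no assumption about rates: it is the difference between a normal approximation and the named test. The range around 61% does rest on assumptions. It runs from 29% to 74% for a halving at control rates of 30% to 60%, and from 47% to 36% when 10% to 20% of remaining patients fail for drug-unrelated reasons. The documents supply no rate for the composite in level 3 or 4 patients, so no single corrected power exists.

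**What to change.** In Protocol 8.2 and SAP 4, keep 132 patients and:

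- state the control and target rates for the composite actually analysed, in level 3 or 4 patients, and the basis for each, including a summary of the initial data;
- restore the target rate in SAP 4;
- replace the single 70% with exact two-sided Fisher power (about 61% at 50% v 25%), tabulated over control rates both below and above 50% and over a stated range of drug-unrelated failure;
- confirm which protocol version and which definition of the composite the planning rate refers to.

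The cost is wording only. The downside is that the stated power becomes less favourable.

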Although the interim analysis will utilize masked treatment assignments, the O'Brien Fleming group sequential sample size estimation confirms that a single interim look would retain a cumulative exit probability of 70% with a cumulative alpha =0.05 after the final analysis using the target enrollment of 132 (44 per group) to detect a reduction of those reaching the endpoint of treatment failure, which includes advancing to WHO COVID-19 Classification level \geq 6 from 50% (SOC treated) to 25% in either treatment group of SOC plus GLS-1027. Other conditions also qualify a subject as treatment failure include: need for salvage therapy with IL-6 monoclonal antibody; or institution of salvage therapy with dexamethasone (\geq 6 mg/day), withdrawing consent from the study, becoming lost to follow-up, or discontinuation of treatment for any reason other than renal function or pregnancy. This study is not powered to assess statistically significant differences between GLS-1027 doses.

Study assessments:

Adverse events will be monitored and recorded throughout hospitalization from the point of enrollment. Daily assessments of vital signs and clinical laboratory parameters will be reviewed and recorded. Follow-up clinical status will be assessed to Day 56. The first 15 persons enrolled will be included in a pharmacokinetic sub-study assessment to determine elimination of GLS-1027, while trough levels will be monitored throughout the study.

Efficacy will be assessed by evaluating the difference in the proportion of treatment failures by group. Treatment failure will be defined as any of the following:

- 1) progression to WHO COVID-19 classification level of 6 or greater within the 28 days of treatment initiation,
- need for salvage therapy with IL-6 monoclonal antibody; or institution of salvage therapy with dexamethasone (≥ 6 mg/day),
- 3) withdrawing consent from the study,
- 4) becoming lost to follow-up, or
- 5) discontinuation of treatment for any reason other than renal function or pregnancy.

A masked interim analysis will be performed when 22 subjects in each group have been assessed for the primary endpoint of treatment failure. The interim analysis is intended for blinded safety assessment. Unless safety is of concern, the study will not be stopped for futility and enrollment will continue to the targeted sample size of 132.

Study population:

Inclusion criteria for enrollment:

- 1. Age 18 years or older
- 2. Able to provide consent

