8.6 Efficacy Analysis

The primary endpoint is treatment failure which is defined as any subject who achieved WHO level \ge 6 (intubation and mechanical ventilation, requirement for ECMO, or death) within 28 days of initiating treatment or who meet the following reasons for treatment failure:

- Receiving salvage therapy with either an IL-6 monoclonal antibody or for those who are prescribed daily dexamethasone starting 72 hours or later after the 1st dose of study drug within the 28-day primary treatment period.
- Lost to follow-up through hospital transfer, within the 28-day primary treatment period.
- Discontinuation of study drug for any cause prior to discharge will be considered as a treatment failure, except for those for whom study drug was suspended due to a decrease in renal function (creatinine clearance of < 60 mL/min), and those become pregnant during treatment. These subjects will be followed for the primary endpoint for up to 28 days post enrollment, and for up to 56 days for safety.

Subjects who complete 28 days of treatment but remain hospitalized without increase in WHO COVID-19 Classification level to ≥ 6 , will not considered be as treatment failures with respect to the primary endpoint.

The proportion of subjects in each treatment group who reach the study endpoint of treatment failure by 28 days will be compared to placebo using Fisher's Exact 2-sided test of proportions. Additionally, the frequency for each outcome (intubation, ECMO, death) will be determined within each group. The ITT, mITT and PP analysis populations will be used to analyze the primary endpoint.

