5. GENERAL ANALYSIS CONSIDERATIONS

The statistical analysis results will be reported using tables, listings, and figures (TLFs). Summaries of continuous variables will display means, standard deviations (SDs), medians, minimums, maximums, and the number of observations. Summaries of categorical variables will display frequency counts and percentages.

CONFIDENTIAL Page 8 03DEC2021

^h Record maximal daily level of PEEP and delivered FiO2 by mechanical ventilation, if participant is receiving mechanical ventilation

All analyses will be performed using SAS® Version 9.4 or higher.

A masked interim analysis will be performed when 22 subjects in each group have been assessed for the primary endpoint of treatment failure. The primary goals of this analysis are to review blinded safety to ensure that GLS-1027 has no concerns or causes worsening conditions. Unless safety is of concern, the study will not be stopped for futility and enrollment will continue to the targeted sample size of 132.

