8.2. Analysis of the Primary Efficacy Endpoint

The proportion of subjects in each treatment group who reach the study endpoint of treatment failure by 28 days will be compared to placebo using Fisher's Exact 2-sided test of proportions. Additionally, the frequency for each outcome (intubation, ECMO, death) will be determined within each group. The ITT, mITT and PP analysis populations will be used to analyze the primary endpoint.

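### The stated 70% power belongs to a large-sample test; the planned two-sided Fisher exact test has about 61% with 44 per group at 50% v 25%

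*SAP*

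**What the plan says.** SAP 4, in the same words as Protocol 8.2, bases the sample size on Fisher's "Exact two-sided test for 2 proportions using NQuery 8". It then says an O'Brien-Fleming group sequential estimation confirms that "a single interim look would retain a cumulative exit probability of 70% with a cumulative alpha =0.05 after the final analysis", with 132 participants, 44 per group. The protocol synopsis carries the same 70% sentence. Protocol 8.2 gives the effect to be detected as a fall in treatment failure "from 50% (SOC treated) to 25% in either treatment group of SOC plus GLS-1027". SAP 4 repeats the 50% but gives no treated rate.

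For the analysis, Protocol 8.6 says the proportions that "reach the study endpoint of treatment failure by 28 days will be compared to placebo using" Fisher's two-sided test, and SAP 8.2 likewise names Fisher's "Exact 2-sided test of proportions". Neither document gives a power for that test.

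On the interim look, the protocol synopsis says "The interim analysis is intended for blinded safety assessment", and SAP 5 says that unless safety is of concern "the study will not be stopped for futility and enrollment will continue to the targeted sample size of 132". On multiplicity, SAP 4 adds a step that the protocol does not have: "A gate-keeping method will be used to compare the highest dose to placebo first". Footnote 2 of Table 14.2.1.1 in SAP Appendix C applies it, giving a p-value for 120 mg only if 360 mg is significant.

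**The concern.** Fisher's exact test is conservative at this sample size, so its power is usually well below that of a z-test or an uncorrected chi-square test. A single 70% placed directly after the statement that the sample size rests on Fisher will be read as the power of the planned analysis. If it belongs to a different test, the plan overstates its chance of detecting the effect it was designed for.

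What is at stake is how a negative result is read. A non-significant 360 mg comparison would be judged against a 30% chance of a miss when the true figure is nearer 40%.

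**Working it through.** **Inputs.** 44 per group, 1:1:1 (Protocol 8.2 and 8.3, SAP 4). Rates 0.50 v 0.25 (Protocol 8.2). Two-sided 0.05. One look at 22 per group, information fraction 0.5 (Protocol 8.8, SAP 5). 360 mg v placebo tested first at the full 0.05 (SAP 4).

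**Step 1: reproduce the 70%.** With unpooled variance:

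- SE = √(0.50×0.50/44 + 0.25×0.75/44) = √(0.4375/44) = 0.0997
- Drift = 0.25/0.0997 = 2.507
- Fixed-design power = Φ(2.507 − 1.960) = 70.8%
- Two-look O'Brien-Fleming, classical bounds 2.797 and 1.977: 70.4% over both looks. The final look alone gives Φ(2.507 − 1.977) = 70.2%
- Two-look with Lan-DeMets spending, bounds 2.963 and 1.969: 70.6%

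So the 70% reproduces as a normal-approximation group sequential figure. The uncorrected Pearson chi-square test, by exact enumeration, also has 70.1%.

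**Step 2: power of the named test.** Power is the sum of Bin(a; 44, 0.50) × Bin(b; 44, 0.25) over all 45 × 45 outcomes (a, b) with a two-sided Fisher p ≤ 0.05.

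- Result: 0.6106, or 61.1%
- Shortfall: 70 − 61.1 = 8.9 points
- Type II error: 1 − 0.611 = 38.9%, against 30%

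**Step 3: where the gap comes from.** The actual size of the Fisher test at nominal 0.05, by the same enumeration:

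| Common failure rate | Fisher size | Uncorrected chi-square size |
|---|---|---|
| 25% | 2.6% | 5.3% |
| 30% | 2.8% | 5.3% |
| 40% | 2.9% | 5.2% |
| 50% | 2.5% | 4.4% |

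The interim look is not the cause. In the z model it moves power only from 70.2% (final look alone) to 70.4% (both looks). With Fisher tests at both looks, power is 61.2% at Lan-DeMets levels (0.00305 and 0.049) and 59.8% at classical levels (about 0.0052 and 0.048).

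**Step 4: what it means at the boundary.** With 22/44 failures on placebo and a final level of 0.05, 12/44 on treatment gives p = 0.0481 (significant) and 13/44 gives p = 0.0808 (not significant). At the classical O'Brien-Fleming final level (bound 1.977, about 0.0480), 12/44 would also just miss.

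**Step 5: the gated 120 mg test.** If both doses truly have 25% failure, allowing for the shared placebo group, the chance that both comparisons are significant is 44.9%. That is 61.1% for 360 mg, then 0.449/0.611 = 73.5% for 120 mg given that 360 mg is significant.

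**Step 6: sample size at which Fisher reaches 70%.** 51 per group gives 69.0% and 52 gives 70.3%, so 156 in total against 132. This shows the size of the gap; it is not a request for more patients.

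**The case against.** The 61.1% is hard to dispute. The objections concern how the 70% should be read and how far the fix should go.

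- **The 70% is labelled O'Brien-Fleming and reproduces as such.** True: this is a mismatch of method, not a slip in arithmetic. But the text presents that calculation as confirming a size just said to rest on Fisher, and gives no other power.
- **The protocol speaks of either treatment group and has no gate.** If that means at least one dose significant, with both truly at 25% and each tested at unadjusted 0.05, Fisher power is 77.2%; at 0.025 each it is 66.7%. Neither is 70%, and under the SAP's gate the first test is the single 360 mg comparison.
- **The rates are uncertain.** The SAP applies the 50% to a wider composite than the protocol does, and gives no 25%. Fisher power is 45% at 40% v 20%, 68% at 55% v 27.5% and 74% at 60% v 30%. This stands as a reason to state the 61% as conditional on 50% v 25%.
- **Stating a final level of 0.05 is a design choice.** The documents give only a cumulative alpha. But with a masked look and no efficacy stop, nothing is spent, so 0.05 fits the plan. The stricter final level of about 0.048 would lower Fisher power to 59.6%.
- **132 is a minimum in parts of the protocol.** Sections 3.2 and 8.8 say at least that number, and 7.3.2 allows an increase to study dose response. The stated power is nevertheless for 44 per group.
- **It is a proof of concept.** A modest power target is acceptable, but it should still be the power of the planned test.

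**Conclusion.** The concern holds. For 360 mg v placebo the planned analysis has about 61% power, not 70%, given 44 per group, true failure rates of 50% and 25%, and a final two-sided level of 0.05. No reading examined gives 70% for the two-sided Fisher test: retaining an O'Brien-Fleming look leaves it at 59.8% to 61.2%, and counting either dose gives 77.2% or 66.7%.

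The 44.9% for 120 mg is a disclosure, not a second error: neither document promises 70% for the gated test, and the figure further assumes that both doses truly have 25% failure. The power statement should be corrected because a null result will be read against it.

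**What to change.** In the protocol synopsis, Protocol 8.2 and SAP 4, replace the O'Brien-Fleming sentence with text such as:

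> With 44 per group, a two-sided Fisher exact test at 0.05 has about 61% power for 360 mg v placebo if the failure rates are 25% and 50%. The masked interim look is a safety review with no efficacy stop; it spends no alpha, and the final test is at two-sided 0.05.

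Give the 25% treated rate in SAP 4 as well. Reconcile the protocol's reference to either dose with the SAP's gate by adding:

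> The chance of declaring 120 mg through the gate is about 45% if both doses truly have a 25% failure rate.

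The cost is wording in three places and a less favourable stated power. Sample size, test, overall alpha of 0.05 and endpoint do not change.
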